Objectives/Outcomes:	Aim 1. To compare the two study conditions in terms of: a) XR-NTX treatment adherence; b) opioid use; c) criminal activity; d) re-arrest; e) re-incarceration; and f) HIV risk-behaviors (i. needle use; and ii. risky sexual behaviors). Aim 2. To determine if the number of months of post-release XR-NTX treatment is related to outcomes (a-f above), and if so, is there a point at which XR-NTX v. Non-XR-NTX equilibrates. Such a finding could be potentially important because it would be informative about the needed length of XR-NTX treatment
Study Design:	The study is a parallel two-group randomized controlled trial in which 240 (120 per condition) incarcerated men and women will be randomly assigned within gender to one of two conditions: Condition 1. XR-NTX-OTx. One injection of XR-NTX in prison, followed by 6 monthly injections post-release at a community opioid treatment program. Condition 2. XR-NTX+ MMTx. One injection of XR-NTX in prison followed by 6 monthly injections post-release at the participant's place of residence utilizing mobile medical treatment. All participants will be evaluated at 1-, 2-, 3-, 4-, 5-, 6-, 7- (safety visit) and 12-months after release from prison.
Subjects:	Inclusion Criteria: (1) adult male or female inmate at BCF, DRCF, BCCC, MCIW CMCF, MCTC, or RCI and be eligible for release within 30 days; (2) history of opiate disorder [meeting DSM-5 criteria of dependence at the time of incarceration; individuals who do not meet criteria at time of incarceration and become addicted during incarceration will be eligible]. Inmates not meeting the opioid-dependence criterion will be eligible if they were treated in an opioid agonist treatment program during the year before incarceration (3) suitability for XR-NTX treatment as determined by medical evaluation; (4) currently opioid-free by history, with negative urine for all opioids and no signs of opiate withdrawal; (5) willingness to enroll in XR-NTX treatment in prison [not currently in or planning to pursue agonist (methadone, buprenorphine) treatment at release]; and (6) planning to live in Baltimore City or County (individuals planning to live outside of Baltimore City/county will be allowed to participate as long as they agree to travel to the treatment clinic if randomized to OTX. Exclusion Criteria: (1) Liver function test levels greater than three times normal (if a blood sample is not obtained at baseline participants will still be eligible for participation); (2) Active medical illness that may make participation hazardous (e.g., unstable diabetes, heart disease). Adequately treated medical conditions are acceptable; (3) Untreated psychiatric disorder that may make participation hazardous (e.g., untreated psychosis, bipolar disorder with mania). Adequately treated psychiatric disorders and appropriate psychotropic medications will be allowed; (4) History of allergic reaction to XR-NTX; (5) Current chronic pain diagnosis for which opioids are prescribed; (6) creatinine above normal limits; (7) pregnancy (for women); (8) Breast-feeding (for women); (9) suicidal ideation (within the past 6-months); and (10) Body Mass Index (BMI) > 40
Study Product:	Vivitrol ® (naltrexone for extended release injectable suspension) 380 mg per month delivered in monthly intramuscular injections
Duration:	7 months (1 injection in prison and 6 in the community.
Sample Size:	240 subjects
Statistical Methodology:	A Generalized Linear Mixed Model (GLiMM) will be used to conduct all analyses.

List of Abbreviations

Abbreviation/specialist term	Explanation
XR-NTx	Long acting naltrexone
DSM-V	Diagnostic and Statistical Manual of Mental Disorders, Fifth Edition

1.0 SPECIFIC AIMS

Heroin use has risen significantly over the past 11 years¹ with heroin overdoses increasing by 23%.² Opioid use disorders are a severe problem among jail and prison inmates throughout the world.³⁻⁷ In the United States, there are over 1.5 million state and federal prisoners,⁸ of whom an estimated 12-15% have histories of OUDs.⁹ Moreover, scarce resources are provided for corrections-based substance use treatment in many nations, and many inmates with OUDs remain untreated;^{7,10} and less than .1% receive agonist treatment.¹¹ Correctional health officials, treatment providers, and policy makers need innovative, effective, and cost-beneficial approaches to help inmates with OUD successfully transition to the community.

We recently completed a Phase 4 pilot, open-label study of long-acting injectable naltrexone (XR-NTX), funded by Alkermes, with prisoners with pre-incarceration OUD. In this study, involving one XR-NTX injection in prison followed by 6 monthly injections in the community, XR-NTX was feasible; all 27 participants got their first injection.¹² XR-NTX was acceptable to correctional officials; it did not disrupt security and other prison routines and there was no concern about its diversion. An expected benefit of XR-NTX was opioid blockade for 30 days; there were no overdoses in the first month post-release. However, an important challenge was that while 78% of participants received their first community injection, only 37% received their 5th and 6th injections. In our multi-site study of parolees/probationers funded by NIDA,¹³ 308 participants were randomized to XR-NTX across five sites in which 95% received the first injection; 65% received their 5th and 59% received their 6th injections. XR-NTX adherence rates were higher in parolees and probationers and roughly equal to opioid agonist treatment but still dropped off by month 6. Also, most parole/probation participants were recruited from community treatment programs and were nearing completion of treatment at study entry, which meant that they were more likely to have more stable lives than newly released prisoners. These results and many stressors faced by newly released prisoners, noted below, suggest that enhancements to prison initiation of XR-NTX are needed in order to ensure continued adherence to XR-NTX treatment.

Many of our XR-NTX prisoners left treatment because of the need for stable housing, legitimate employment, child care, securing health benefits, addressing medical and psychiatric issues, and meeting requirements regarding criminal justice supervision interfered with continued treatment. Thus, a **Mobile Medical Treatment approach** that will provide medication at the client's place of residence might improve adherence and expand capacity and treatment access by reducing travel time and cost.¹⁴ Many programs have implemented mobile services, including for opioid addiction using LAAM,¹⁵ methadone,^{14,16,17} HIV education and testing,¹⁸ HIV treatment,¹⁹ for mental health services²⁰ and cancer information and support.^{21,22} In summary, the above studies were successful in increasing access and engaging clients in treatment.

1.1. Design

The proposed study is a parallel two-group randomized controlled trial in which 120 incarcerated men and 120 incarcerated women will be randomly assigned within gender, to one of two conditions: (1) **XR-NTX+ MMTx**. One injection of XR-NTX in prison followed by 6 monthly injections post-release at the participants's place of residence utilizing mobile medical treatment; or, (2) **XR-NTX-OTx**. One injection of XR-NTX in prison, followed by 6 monthly injections post-release at a community opioid treatment program. All participants will be confirmed opiate-free prior to XR-NTX injection, and evaluated at 1-, 2-, 3-, 4-, 5-, 6-, 7- (safety visit) and 12-months after release from prison.

1.2. Specific Aims

Aim1. To compare the two study conditions in terms of: (a) XR-NTX treatment adherence; (b) opioid use; (c) criminal activity; (d) re-arrest; (e) re-incarceration; and (f) HIV risk-behaviors (i. needle use; and ii. risky sexual behaviors).

Aim 2. To determine if the number of months of post-release XR-NTX treatment is related to outcomes (a)-(f), and if so, is there a point at which XR-NTX v. Non-XR-NTX equilibrates. Such a finding could be potentially important because it would be informative about the needed length of XR-NTX treatment.

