5.7. XR-NTX Treatment in the Community

5.7.1. Glenwood Life Counseling Center for XR-NTX injections. The participants randomized to XR-NTX-OTx will go to GLCC only to receive injections under the direction of [name] and the study nurse from prison in order to ensure continuity of care for those receiving XR-NTX in the community (injections will occur every 28 days). The study RA will be in close contact upon release and will provide the client with reminder calls and/or visits prior to each XR-NTX appointment. Prior to each injection (at GLCC and place of residence), the nurse will administer: 1) a drug use questionnaire, and 2) an instant urine drug screening test. If negative for opioid use participants will be administered XR-NTX. If the participant reports using opioids in the past 7-10 days or tests positive on the urine drug screen they will not be administered XR-NTX (see procedures below for missed XR-NTX injections). Once the participant receives the injection, he/she will be monitored for up to 1½ hours. In addition, the nurse will provide the participant with the Naltrexone Medication Card, and tell the participant that he/she should keep it at all times. The nurse or physician will follow the same procedures as in prison.

5.7.2. Place of Residence for XR-NTX injections. For those randomized to receive XR-NTX at their place of residence, specific procedures will be implemented. First, the study nurse will be accompanied by the study RA so two staff members are always physically present. The study RA will confirm the place of residence prior to release from prison using our locator form. Contact will be made with the participant immediately following prison release and subsequently one week before each scheduled injection to verify his/her home address as

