
5.7.3. Missed XR-NTX Injections. Participants who miss a monthly appointment will be contacted by the study RA within 24 hours of missing their appointment. The participant will be strongly encouraged to receive their next injection. If they miss a dose and return for a subsequent dose more than 7 days after their missed scheduled injection they will receive the following: 1) drug use questionnaire; 2) urine rapid test; and 3) naloxone challenge before the naltrexone injection. Everyone who reports opioid use or has a positive urine test for opioids during days 29-37 will be given the naloxone test and then the oral naltrexone (12.5mg) prior to the Vivitrol injection. If a participant misses a scheduled injection, he/she will have up to 37 days to receive their next XR-NTX injection. We will also record the number of successful rescues and number of delayed returns to XR-NTX treatment. Participants will no longer receive XR-NTX if they become incarcerated in jail or prison (if incarcerated less than 37 days, they will still be eligible receive their injection).

5.7.4. Withdrawal from Naltrexone: Treatment Safety. Participants may voluntarily stop taking XR-NTX doses at any time without penalty. Naltrexone is an opioid antagonist with no opioid agonist properties and no withdrawal upon discontinuation. Potential side effects relate to the medication itself and to the injection. The most frequent side effects of the medication include opioid withdrawal symptoms for those participants who still have some trace of opioids in their system. There had been reports of increased liver enzymes in individuals receiving high doses of oral NTX in a study of obesity. For this reason, we have an exclusion criterion regarding elevated liver function tests at baseline. The injection can lead to local irritation, infection, and potentially abscesses, which in the most extreme circumstance may require surgical debridement. Participants receiving XR-NTX who require acute treatment of pain will be told that they need to inform their physicians that they are on XR-NTX because XR-NTX is an antagonist and will block the effects of opioid-agonist pain medications. In addition, each participant will also receive a laminated card that indicates they are on XR-NTX that can be provided to their health care provider.

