5.8. Measures

Assessment of participant characteristics and/or performance will involve a multidimensional set of instruments administered by trained research interviewers. See **Figure 2**, for a schematic of measures and when they are administered. Sources of information will include: (1) self-report; (2) official records; (3) urine drug screening results; and (4) treatment program records. Assessment at baseline will provide information on participant characteristics and pre-incarceration histories of substance use, substance use treatment, crime, incarceration, and HIV risk behavior. Participants in both conditions will be paid \$50 cash for each follow-up visit. Participants

will not be paid for baseline assessments in prison due to the fact that such payments may be viewed as coercion.

5.8.1. XR-NTX Adherence. Data on post-release treatment status will be obtained from GLCC records. Treatment status will be measured at each follow-up point by whether or not a participant received an injection of XR-NTX at each follow-up point (yes v. no). We will also collect data on whether a person entered outpatient treatment (yes v. no) and the type of services utilized. Treatment duration for individuals who end treatment will be calculated based on the last date of clinic attendance (if a participant fails to receive his/her injection by day 37 s/he would be considered a drop-out). Thirty seven days is used in our current XR-NTX studies as this is how long the medication typically protects the participant. We will also collect data on whether or not participants entered other types of treatment. Follow-up assessments will collect self-report data on reasons why participants entered, did not enter, or dropped out of treatment.

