5.8.2. Addiction Severity Index (ASI) with Timeline Follow-Back (TLFB). The ASI is a standardized 40-60 minute measure widely used in research to quantify problem areas in substance-using populations.^{89,90} This instrument has excellent inter-rater and test-retest reliability.^{89,90} We will also collect data on substance use frequency and criminal activity to cover the entirety of the follow-up periods post-baseline. In addition, we will use the DSM-5 opioid-related-disorder classification⁹¹ to assess opioid use severity (mild, moderate, severe). In addition to the ASI, we will collect baseline data on crime severity which is determined on the basis of a 7-point scale (a higher number indicating greater severity of criminal involvement) and classifies crime severity according to the most serious level of criminal activity in their lifetime prior to the index incarceration.⁹²

5.8.3. Biological Assays. Urine will be tested on-site with CLIA waived QuikScreen cups using an immunochromatographic assay for rapid (2-5 minute) qualitative results based on SAMHSA-standard cutoffs for alcohol (20mg/dl or 0.02% BAC), amphetamine/methamphetamine (1,000 ng/ml), cannabis (50 ng/ml), cocaine/ benzoylecgonine (150 ng/ml), and opiates/morphine (2000 ng/ml). In addition, we will test for methadone and buprenorphine, and for commonly abused prescription drugs (*oxycodone, hydrocodone, and codeine*) (100 ng/ml), and for *Fentanyl* (10ng/ml). Results will be used as outcome measures of heroin and other opioid use as well as to check on the validity of self-reported drug use information. Urine samples will not be obtained on the approximately 10% of participants who we expect to be re-incarcerated. Those participants in methadone or buprenorphine treatment who screen positive only on their respective treatment medication will be counted as negative for their urine drug screening results.

5.8.4. Risk Assessment of Battery (RAB). This self-administered questionnaire, designed to identify individuals engaging in acts that could transmit HIV and other infectious diseases,⁹³ contains 45-items consisting of three scales: a drug risk, sexual behavior risk, and an overall scale.

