5.9. Study Aims, Hypothesis, Rationale

5.9.1. Aims. The proposed study has two specific aims: **Aim 1.** To compare the two study conditions in terms of: a) XR-NTX treatment adherence; b) opioid use; c) criminal activity; d) re-arrest; e) re-incarceration; and f) HIV risk-behaviors (i. needle use; ii. risky sexual behaviors). **Aim 2.** To determine if the number of months of post-release XR-NTX treatment is related to outcome (a-f above), and if so, is there a point at which XR-NTX v. Non-XR-NTX equilibrates.

5.9.2. Hypothesis. Based on data from the research team's current studies (see above), It is anticipated that the XR-NTX+MMTx condition will have superior outcomes compared to the XR-NTX+OTx condition in terms of outcomes (a)-(f).

5.9.3. Rationale. We are not aware of RCTs using mobile medical treatment for the provision of XR-NTX. However, based on studies utilizing mobile treatment for HIV services, and methadone, which increased access, engagement, and retention, we believe the provision of medical treatment, provided at a participant's place of residence, is expected to yield better adherence, subsequently, improving outcomes mentioned above. If we find a point of equilibration it will tell us how many months we will need to provide mobile treatment (XR-NTX) and at what point it impacts on outcomes-significant given the cost of the medication. It is difficult to provide firm conjectures on this latter question given the lack of research in this area.

Figure 2: Data Collection Schedule

Measures	Source	Interval	Operational Definition
Aim 1: Outcomes (a)-(f)			
a. XR-NTX adherence	Clinic records	B, 1-6	• # of injections due/completed
b. opioid use	ASI/TLFB/UDS	B, 1-6, 7, 12	• days of opioid use • positive opioid urine drug screen
c. criminal activity	ASI/TLFB	B, 1-6, 7,12	• days of crime
d. re-arrest	Official records	12	• time to re-arrest
e. re-incarceration	Official records	12	• time to re-incarceration
f. HIV risk behaviors	RAB/TLFB	B, 1-6, 7,12	• scored 0-22 (higher risk) • scored 0-18 (higher risk)
i. needle use			
ii. risky sex behaviors			
Aim 2: Outcomes (a)-(f)			
(a)-(f) equilibrates	Above	1-6,12	Time to relapse
Supplementary			
other treatment	ASI	B, 1-6, 7, 12	• Days in other treatment
opioid overdose	OOS	B, 1-6, 7, 12	• # of times overdosed
opioid craving	VAS	B, 1-6, 7, 12	• 0-100 (higher cravings)
Quality of Life	QOL	B, 1-6, 7, 12	

Figure 3: Biometric Measures

Measures	Data Collection Point						

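### Aim 2 relates non-randomised months of XR-NTX to outcomes that include the injection count itself and an event that stops injections, yet the protocol reads the result as the treatment length needed

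*Combined protocol and SAP*

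**What the plan says.** Section 1.2 gives Aim 2 as "To determine if the number of months of post-release XR-NTX treatment is related to outcomes (a)-(f", and asks whether there is a point at which XR-NTX and Non-XR-NTX equilibrate. The synopsis and sections 4.1 and 5.9.1 repeat it. Section 1.2 says cautiously that such a finding could matter for the length of treatment. Section 3.0 goes further and says it will be evidence on the number of injections needed. Section 5.9.3 says an equilibration point will show how many months to provide.

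Only the place of delivery is randomised. Both arms are planned one prison injection and six community injections, and section 9.5 confirms that no arm goes without the drug.

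- **Outcome (a).** Figure 2 defines it as the number "of injections due/completed".
- **Incarceration.** Section 5.7.3: "Participants will no longer receive XR-NTX if they become incarcerated in jail or prison", with an exception for stays under 37 days.
- **Opioid use.** Section 5.7.1: a participant who reports recent use or "tests positive on the urine drug screen they will not be administered XR-NTX", with a pointer to the missed-injection procedure. That procedure, in 5.7.3, says of a missed injection that "he/she will have up to 37 days to receive their next XR-NTX injection", and adds: "Everyone who reports opioid use or has a positive urine test for opioids during days 29-37 will be given the naloxone test", followed by oral naltrexone before the injection.
- **Model.** Section 6.4 has one treatment variable, Treatment Condition, and no term for months of XR-NTX. For Aim 2, Figure 2 lists months 1-6 and 12 and time to relapse; relapse is not defined.
- **Duration.** Section 5.8.1: "Treatment duration for individuals who end treatment will be calculated based on the last date of clinic attendance".

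**The concern.** The exposure is something participants accumulate, and some of the outcomes decide how much they accumulate. A person re-incarcerated in month 2 for longer than the exception allows cannot reach six injections. That person is then counted as having had little drug and a bad outcome, whatever the drug does. Figure 2 puts Aim 2 outcomes in months 1-6, the same months in which injections accrue, so nothing in the plan prevents a same-window analysis. Section 1.0 also says that pilot participants left treatment over housing, employment, psychiatric and supervision problems, which plausibly predict outcome too.

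At stake is the practical message. An association produced partly by stopping rules could be published as evidence on how long to treat.

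**Working it through.** **1. The plan's own figure.** Section 6.7 states f² = .037 for 80% power at N=216. A noncentral F with 1 and 214 degrees of freedom gives 0.0367, and power 0.8035 at .037, so it reproduces. It concerns Treatment Condition, that is Aim 1. Nothing is stated for Aim 2.

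**2. Outcome (a).** Exposure is injections received; the outcome is injections completed out of those due. With six due for everyone, the correlation is 1 by construction.

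**3. Re-incarceration, by arithmetic.** Suppose XR-NTX has no effect, everyone has the same monthly incarceration risk h, and every stay is 37 days or more. A six-injection completer cannot have been incarcerated in months 1-6.

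- Completers' 12-month risk: 1-(1-h)^6
- Overall 12-month risk: 1-(1-h)^12
- Others' risk: (overall - k × completers) / (1-k), where k is the share completing six

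The pilot (section 2.7.3) had 10/27 = 37% at injection six. Assumed losses of 10% a month after opioid use and 5% a month from voluntary stopping give k = (0.90 × 0.95 × (1-h))^6, close to that figure. Section 5.8.3 supplies a rate without a period: "Urine samples will not be obtained on the approximately 10% of participants who we expect to be re-incarcerated". Read as 12 months, h = 1-0.9^(1/12) = 0.87%. The 2% a month row is an assumption, shown for range.

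| h | k | Overall | Completers | Others |
|---|---|---|---|---|
| 0.87% a month | 0.371 | 10.0% | 5.1% | (0.100 - 0.371 × 0.051)/0.629 = 12.9% |
| 2% a month | 0.346 | 21.5% | 11.4% | (0.215 - 0.346 × 0.114)/0.654 = 26.9% |

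The rule alone makes completers look less than half as likely to be re-incarcerated.

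**4. How often this would be significant.** Null simulation: N=216, 12-month re-incarceration (yes/no) correlated with community injections (0-6), two-sided 0.05, retention of about 35-38% at injection six.

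| Re-incarceration | No stays under 37 days | Half under 37 days |
|---|---|---|
| 10% a year | 43% | 16% |
| 2% a month | 74% | 23% |

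Repeat runs agree within about three percentage points. Using only re-incarcerations after month 6, among people event-free at that point, gives 4-6% when everyone has equal risk.

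**5. Opioid use.** The feedback depends on the share who, after an injection is withheld, return and receive it on days 29-37. With assumed use of 5-15% a month and voluntary stopping of 5%, the null false-positive rate is 100% at 0% return, 95-100% at 50%, and 5-10% at 90%. The documents do not state this share, so no single size can be given.

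**6. Outcomes (c), (d) and (f).** No rule stops injections because of crime days, arrest or risk score. Any link runs through incarceration, opioid use or shared prognosis. Nothing was computed for these.

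**The case against.** The best defence is that Aim 2 asks only whether months are related to outcomes. Section 1.2 is cautious, section 5.9.3 concedes that firm conjectures are difficult, and the hypothesis in 5.9.2 covers only the comparison of arms. No section plans a correlation of total injections with re-incarceration. This stands to the extent that no false-positive rate can be attributed to the plan as written.

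A reader might infer that the re-incarceration result would nearly always be falsely significant. Rates up to 85% (10% a year) or 99% (2% a month) do arise, but only where 60-68% of participants receive injection six, against 37% in the protocol's own prisoner pilot.

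A reader might also infer that 5.7.1 and 5.7.3 flatly contradict each other on injection after opioid use. The pointer in 5.7.1 allows them to be read as consecutive steps: withheld at that visit, then the missed-injection procedure. The sponsor should clarify how they fit together, because the bias for outcome (b) turns on it.

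Aim 2 might instead be read as condition by time (6.4.3), since 5.9.3 speaks of months of mobile treatment. That contrast is randomised, but Aim 2 itself asks about months of XR-NTX, and 6.4 contains no such term.

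The clinic-attendance wording in 5.8.1 does not fit the 120 of 240 participants assigned to injections at home. It is probably a slip, since the same section records each injection. What the defence does not answer is the circularity of (a), the incarceration rule, or the needed-length statements in 3.0 and 5.9.3.

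**Conclusion.** The concern holds in limited form. The circularity of outcome (a) and the feedback from incarceration follow from the documents without any simulation. The size for re-incarceration, 16-43% or 23-74% false positives, rests on assumed monthly rates, pilot-like retention, the share of short stays, and a test chosen for illustration. It is not a forecast. The opioid-use feedback is conditional on the unstated return share, and for (c), (d) and (f) only indirect paths exist.

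A reader might infer that the randomised comparison is compromised. It is not: Aim 1 compares arms as assigned and does not use months received. What cannot be supported is any conclusion about the number of months or injections needed, because no randomised contrast in treatment length exists.

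**What to change.** 1. Drop outcome (a) from Aim 2.
2. Never relate injections to outcomes in the same window. Define exposure identically in both arms, from injection dates up to a fixed landmark such as day 183 after release. Use only later outcomes, among people event-free at the landmark. Do not count later injections: the sixth falls on day 158-168 at 28-day intervals (6 × 28 - 10 to 6 × 28), but can fall on day 212-222 at 37-day intervals. A lagged model, with the outcome in month t on injections received by visit t-1, is an acceptable alternative.
3. Show results with and without adjustment for earlier opioid use, which may be both a confounder and a mediator.
4. Report Aim 2 as a non-randomised association. Delete or soften the needed-length statements in the synopsis and sections 1.2, 3.0 and 5.9.3. Delete the XR-NTX v. Non-XR-NTX wording, or define it as time on versus off drug.

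**Cost.** These are wording and analysis changes. The landmark loses about half of the 12-month re-incarcerations among 240 participants: 240 × (1-0.98^6) = 27 of 240 × (1-0.98^12) = 52 at 2% a month, or 240 × (1-0.9^0.5) = 12 of 24 at 10% a year. It has low power, cannot locate equilibration during treatment, and leaves person-level confounding. With individual risk varying (log-normal SD 1, 50% return, both assumed), null false-positive rates for re-incarceration after the landmark are still 12-24% unadjusted.

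**Separate minor point (6.9, 6.10).** Distance to the clinic is recorded only for the clinic ('TAU') arm, so distance by condition cannot be estimated from the field as recorded. Compute it in both arms from an address recorded before assignment; this may need an added baseline item.
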